4.1.3.2 Toxicology

Local toxicity

A 9-month (39 weeks) chronic repeat-dose toxicology study was done to determine the potential toxicity, antigenicity, and toxicokinetic profile of APL-2 when administered to cynomolgus monkeys by IVT injection every 4 weeks for 36 consecutive weeks at doses of 3.1, 12.4, and 24.8 mg/eye.

All animals survived through to Test Week 39. There were no test article effects on clinical observations, body weights, food consumption, hematology, clinical chemistry, CH50, macroscopic pathology or organ weights. APL-2 was minimally antigenic as evidenced by one mid-dose monkey had a marginal titer of 1:20 to APL-2 during week 39 and one monkey the high dose group was found to have low titer 1:100 antibodies to APL-2 during week 13 and 1:500 titer during week 39. There were no test article effects on any ophthalmological parameters monitored, which included indirect and slit lamp, spectral domain optical coherence tomography (SD-OCT), electroretinography (ERG), and tonometry.

Two APL-2 mid-dose animals and one APL-2 high-dose animal exhibited marked inflammation post IVT injection in one eye after the first and third injection, respectively. The inflammation gradually diminished in subsequent weeks upon proper treatment with anti-inflammatory drugs and/or antibiotics. These changes are consistent with incidental inflammation associated with IVT injection procedures and were concluded not to be drug-related.

The ERG responses were normal for both eyes of all animals at baseline, and remained within normal limits through Week 39. No drug-related changes in IOP were observed in any group through Week 39. Spectral domain optical coherence tomographic examinations revealed no APL-2 associated retinal changes. Decreases in macular volume, ≥ 1.5 but ≤ 3 and > 3 mm³, were observed in one vehicle control and one high-dose monkey, respectively. Decreased retinal thickness was observed in vehicle control and PEG40 monkeys but not in APL-2 dosed animals. A single mid-dose animal exhibited an increase in central retinal thickness of > 40 μ m.

in the left eye and an increased central retinal thickness ≥ 20 but ≤ 40 μm in the right eye. These changes were not considered APL-2-related.

Histopathological examinations of both eyes from every animal on study revealed no evidence of APL-2 mediated changes. Eyes of both vehicle control and drug treated monkeys were observed to have fibrosis/pigmented macrophages in the vitreous or needle tracks. The incidence and severity of these changes were identical in all groups regardless of agent injected. Histopathological examination of approximately 50 additional tissue/organs from study animals revealed no evidence of APL-2 attributable changes.

The results of this 9-month chronic study in cynomolgus monkeys support the safety of chronic IVT injections of APL-2 at a 4-week interval in man.

Additional toxicology information

APL-2 had no significant effect on hERG action potential *in vitro*. In addition, APL-2 had no effect during *in vivo* assessments of cardiovascular and respiratory parameters or body temperature when administered SC to telemeterized monkeys.

Apellis has assessed APL-2 in repeat-dose subcutaneous (SC) and intravenous (IV) toxicity studies in rabbits and monkeys. In one of these studies a PEG40 group was included to facilitate identification of changes that are likely attributable to the PEG portion of APL-2 as compared to those elicited by either the peptide moiety or the APL-2 molecule *per se*.

The results of studies during which rabbits and monkeys received SC daily doses of APL-2 (0.25, 1, 3, 7, 28, or 140 mg/kg/d) for up to 28-days or 2 intravenous (IV) doses of APL-2 (42 mg/kg) 14 days apart affords support for the projected systemic safety of APL-2 administered by the IVT route in the proposed clinical trials. After 28 days of SC administration or 2 IV doses, there were neither grossly observable nor clinical pathology changes in either species. A primary microscopic change observed at SC doses of 3 mg/kg/d and higher, common to both APL-2 and PEG40 in both species, was multi-tissue macrophage vacuolation.

Administration of other clinically used PEGylated compounds to laboratory species has been associated with macrophage vacuolation which is believed to be a naturally-occurring adaptive change secondary to the clearance of large molecules from the tissues. Although frequently observed, macrophage vacuolation has not been associated with either behavioral or clinical effects in animals nor with adverse events in humans. The repeated SC dose “no observable effect dose” for macrophage vacuolation in both rabbits and monkeys was determined to be approximately 3 mg/kg/d which was associated with a mean maximal serum concentration in monkeys of approximately 500 $\mu\text{g/mL}$ after 28 days of consecutive SC dosing. That no observable effect serum concentration in SC dosed monkeys is approximately 3-fold higher than the maximal serum concentration achieved in monkeys after the initial IVT administration of 24.8 mg/eye and 6 times higher than that achieved after the tenth IVT injection.

Renal tubular degeneration was also observed in some monkeys administered 28 or 140 mg/kg/d of APL-2 by the SC route. Target organ toxicity in the kidney has also been associated with administration of PEG *per se* to animals. Renal tubular degeneration was also observed in monkeys administered PEG40 and this change was comparable to that observed in the high-

dose APL-2 groups; thus, the peptide did not exacerbate findings attributable to PEG40. The daily SC doses associated with renal tubular degeneration in monkeys, 28 and 140 mg/kg/day, result in maximal serum APL-2 concentrations that are 11 and 24 fold, respectively higher than those associated with IVT administration of 24.8 mg/eye.

The remaining toxicological findings in both the rabbit and the monkey, including clinical pathology changes and/or inflammatory reactions at the injection sites, are monitorable in the clinic. In rabbits, SC administration of APL-2 was slightly to mildly immunogenic; however, SC APL-2 was not associated with any observed immunologic effects in monkeys.

APL-2 and PEG40 did not induce genotoxicity under conditions tested. Both agents were negative in a bacterial reverse-mutation assay (Ames test) with and without S9 metabolic activation; negative for the induction of micronuclei in both non-activated and S9-activated test systems in the in vitro mammalian cell micronucleus test using TK6 cells (proficient p53 human lymphocytes) and negative in the in vivo mouse micronucleus assay.

Collectively there were no findings observed during any of the nonclinical studies that would preclude testing of APL-2 in humans. IVT administration did not lead to any drug-related changes at any of the doses tested. SC administration led to much higher systemic APL-2 levels and some kidney toxicity was noted at the two highest SC doses. Most of the findings following daily SC administration were concluded to be the result of the PEG domain, and since PEGylated proteins are often cleared through the kidney, the high-dose changes noted in the kidney with APL-2 are not unexpected due to the presence of PEG40 as part of the APL-2 molecule. Results from the preclinical toxicology program with APL-2 provide good assurance of the safety for the proposed dose of APL-2 in humans by the IVT route of administration. The dose proposed in this study is 15 mg/eye/injection.

4.1.4 Clinical Data

The safety and tolerability of APL-2 following IVT administration in humans was tested in an open label, single dose escalation, Phase I clinical study in patients with wet age-related macular degeneration under protocol POT-CP043014 (NCT02461771), and the draft clinical study report is available. The study was conducted in multiple ophthalmological clinical sites in the US and Australia. A single dose of APL-2 was administered on Day 1 to patients suffering from exudative AMD currently receiving anti-VEGF (vascular endothelial growth factor) standard of care. Three escalating doses of APL-2 administered IVT were studied. Three subjects received 4 mg; 3 subjects received 10 mg, and 7 subjects received 20 mg. No serious adverse events (SAEs) or drug-related adverse events (AEs) of concern were observed. It was concluded that administration of a single dose of APL-2 IVT up to 20 mg is well-tolerated.

4.2 Rationale

4.2.1 Rationale for Doing this Study

The rationale for the use of a complement inhibitor in patients with AMD is based on evidence from both human and animal studies. Human biochemical, genetic, and clinical lines of evidence indicate that the complement system plays a role in the etiology of age-related

macular degeneration (AMD). Complement components including C3, the Membrane Attack Complex (MAC), and Complement Factor H (CFH), are present in drusen and basal laminar deposits in eyes from patients with AMD.^{9,10,11,12} Genetic variants of CFH,^{10,13,14,15,16} C3,^{17,18} Complement Factor I (CFI)¹⁹ and other complement components^{20,21,22} have been associated with altered risks for the development of both the exudative and atrophic forms of AMD. Patients with AMD also have signs of systemic complement activation, exhibiting higher serum levels of Complement Factor B (CFB), C3a, C5a, SC5b-9, C3d, and Ba compared to age-matched controls.^{23,24,25,26}

While there is not yet an anti-complement therapy approved for the treatment of exudative AMD or GA, data from recent clinical studies support the hypothesis that complement inhibition might have an effect on the etiology of age-related macular degeneration. In the Phase I clinical study, ASaP (Potentia Pharmaceuticals, Inc), thinning of the retina occurred in two high dose patients after treatment with the C3 complement inhibitor APL-1 (a.k.a. POT-4 /AL-78898A) despite extensive pre-existing retinal damage and resistance to anti-VEGF therapy.²⁷ Data from the Phase II clinical study Mahalo (Genentech Inc.), provides for the first time evidence of the positive effect of a complement inhibitor (lampalizumab; an anti-factor D molecule) in GA. The study showed that in the subpopulation of GA patients positive for a Complement Factor I (CFI) exploratory biomarker and treated monthly with lampalizumab, GA progression rate decreased by 44% over 18 months.^{28,29}

In the current clinical study a complement C3 inhibitor, APL-2, will be administered to patients with GA. The goal of the study is to assess the safety and tolerability, and to obtain evidence of activity of IVT APL-2 administered monthly or EOM. Results from this study will guide decisions to further develop APL-2 for GA.

4.2.2 Dose Selection

A single dose of 15 mg/100 μ L injection administered monthly or EOM for 12 months will be tested in this study (see [Section 7.3.1](#)). APL-2 was well-tolerated in a panel of animal toxicology studies. A 9-month, repeat-dose GLP study in cynomolgus monkeys was conducted to evaluate the safety of IVT injections of APL-2 at doses up to 24.8 mg/eye at a frequency of one injection every 4 weeks.

In this pivotal chronic toxicological study conducted in monkeys, the No-Effect-Level (NOEL) was established as >24.8 mg of APL-2 delivered intravitreally every 4 weeks for 9 months using a 100 μ L injection. The volume of the human vitreous is approximately 4 mL, which is approximately 2.7-fold larger than the mean vitreous volume of cynomolgus monkeys, 1.5 mL.³⁰ Based on the difference in vitreous volume between man and cynomolgus and the NOEL defined in non-human primates, the human equivalent dose was determined to be 67 mg/eye every 4 weeks. The dose (15 mg/injection) of APL-2 that will be evaluated in this clinical study is expected to result in drug concentrations approximately 4.5 fold lower than the NOEL observed in cynomolgus monkeys.

4.3 Risk/Benefit

The safety monitoring practices employed by this protocol (e.g. complete ophthalmological exam, IOP monitoring, OCT, vital signs, hematology, serum chemistry, urinalysis, and AE questioning) are adequate to protect the subjects' safety.

There are also risks associated with the ophthalmic procedures required for participants in this study. However, these are all standard procedures that are widely performed in ophthalmology.

In the days following any IVT injection, patients are at risk of developing endophthalmitis. If the eye should become red, sensitive to light, painful, or develop a change in vision, the patient will be instructed to seek immediate care from an ophthalmologist. Other risks of IVT injection include traumatic cataract, retinal detachment and hemorrhage.

Transient increased IOP has also been identified as a risk following IVT injections. IOP will be carefully monitored in this study.

The approximately 150 mL of blood (See [Section 9.9](#)) planned for collection from each subject over the 18 months of the study does not pose an undue risk in this patient population.

Based on data available to date, IVT administration of complement C3 inhibitors does not seem to present an unreasonable ophthalmic or systemic risk to humans. In three previous clinical studies involving 72 subjects undergoing local C3 inhibition with the related compound POT-4/AL-78898A, no drug-related SAEs were reported. Also, a Phase I study with APL-2 in patients with wet AMD has completed and no drug-related SAEs have been reported thus far.

Following a routine scheduled interim review of this ongoing POT-CP121614 (FILLY) study, including data as of April 5, 2017, by the Safety Monitoring Committee, an imbalance in new exudation in subjects treated with APL-2 was observed (further details described in an Investigator Brochure Addendum No. 3, 10 April 2017). Higher rates in new exudation were observed in eyes treated with APL-2, particularly monthly. The risk of developing new exudation may be increased in patients with a prior history of exudative AMD in the fellow eye. Visual acuity in subjects who develop new study eye exudation does not appear to differ significantly from those who do not.

There is a potential health benefit for trial participants from receipt of study drug. We propose to administer APL-2 to patients with GA. If efficacious, APL-2 is expected to alter the course of GA and slow its rate of growth.

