1. SYNOPSIS

Study Title A Phase II, Multicenter, Randomized, Single-Masked, Sham-Controlled Study of Safety, Tolerability and Evidence of Activity of Intravitreal APL-2 Therapy in Patients with Geographic Atrophy (GA) – FILLY -

Protocol Number, Version and Date POT-CP121614 / Version 3.0 / 1 May 2017

Investigational Product, Dose and Route of Administration

- APL-2
- 15 mg/100 µL
- Intravitreal (IVT) Injection

Study Arms

Arm		Randomization
APL-2 15 mg/100 µL Monthly for 12 months	AM	2
APL-2 15 mg/100 µL EOM for 12 months	AEOM	2
Sham Monthly for 12 months	SM	1
Sham EOM for 12 months	SEOM	1

EOM = Every-Other-Month

Study Phase and Type Phase II, Multicenter, Randomized, Single-Masked, Sham-Controlled.

Study Objectives The primary objectives of the study are to assess the safety, tolerability and evidence of activity of multiple intravitreal (IVT) injections of APL-2 in subjects with Geographic Atrophy associated with Age-Related Macular Degeneration (AMD)

Number of Subjects and Sites

- 240 subjects (200 evaluable)
- 40 multinational sites.

Inclusion Criteria Unless specified otherwise, ocular specific inclusion criteria apply to the **study eye** only.

1. Male or Female.
2. Age ≥ 50 years.
3. Best corrected visual acuity (BCVA) of 24 letters or better using Early Treatment Diabetic Retinopathy Study (ETDRS) charts (20/320 Snellen equivalent).
4. Diagnosis of GA of the macula secondary to AMD, confirmed within 14 days prior to randomization by the central reading

center (CRC) using Fundus Autofluorescence (FAF) images, as well as the following criteria:

- a. Total GA area must be ≥ 2.5 and ≤ 17.5 mm² (1 and 7 disk areas [DA] respectively), determined by screening images of FAF.
 - b. If GA is multifocal, at least one focal lesion must be ≥ 1.25 mm² (0.5 DA).
 - c. GA can be completely visualized on the macula centered image.
 - d. GA must be able to be photographed in its entirety.
 - e. GA must be able to be measured separately from any areas of peripapillary atrophy as assessed by the CRC.
 - f. Presence of any pattern of hyperautofluorescence in the junctional zone of GA. Absence of hyperautofluorescence (i.e. pattern = none) is exclusionary. See Holz et al. 2007.¹
5. Female subjects must be:
- a. Women of non-child-bearing potential (WONCBP), or
 - b. Women of child-bearing potential (WOCBP) with a negative pregnancy test at screening and must agree to use protocol defined methods of contraception for the duration of the study.

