4.1.1 Age-Related Macular Degeneration

Age-related macular degeneration is the leading cause of severe vision loss in people over the age of 65 in the United States and other Western countries.² In the United States, about 1.75 million people have the advanced forms of AMD.³ The early signs of AMD (drusen and pigmentary changes) are common in individuals over age 65 and precede the advanced forms, which are visually devastating. The advanced forms of AMD are classified into either macular neovascularization (neovascular, wet, or exudative AMD) or GA.

Exudative AMD is characterized by the abnormal growth of choroidal vessels into the subretinal space. The subsequent exudation of fluid, lipid and blood causes retinal edema resulting in vision loss and symptoms of metamorphopsia. The growth of these new vessels is accompanied by the proliferation of fibrous tissue; the continued growth of these fibroblastic lesions into the macula results in progressive, severe and irreversible vision loss.^{4,5} Although exudative AMD is only present in about 10% of all AMD cases, the majority (90%) of the severe rapid visual loss due to advanced AMD is attributable to the development of macular neovascularization (MNV). Without treatment, most affected eyes will develop poor central vision (20/200) within 12 months. Anti-VEGF agents, such as ranibizumab (Lucentis®), aflibercept (Eylea®) and off-label bevacizumab (Avastin®), are the current standard-of-care for the treatment of exudative AMD.

Geographic Atrophy is a disease characterized by thinning and loss of the retinal pigment epithelium (RPE) and concurrent atrophy of photoreceptors and choriocapillaris.^{6,7,8} Clinically, GA is characterized by islands of dead retinal cells in the back of the eye that gradually expand. Although GA can result in significant visual function deficits in reading, night vision, and dark adaptation, and produce dense, irreversible scotomas in the visual field, the initial decline in VA may be relatively limited if the fovea is spared. When the fovea is involved, GA quickly causes blindness. GA is responsible for approximately 20% of all legal cases of blindness in North America with increasing incidence and prevalence owing to a higher life expectancy.⁶ While there is treatment for exudative AMD with anti-VEGF therapies, no therapy exists for GA which is usually bilateral and relentlessly progressive.

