8.2 Safety Monitoring Committee

An external, independent Safety Monitoring Committee (SMC) will review cumulative unmasked safety data and will have the responsibility to conduct a thorough safety assessment after the first 20 subjects have completed the Day 7, Month 2 and Month 6 visits. A key responsibility of the SMC will be to make a recommendation whether to continue, modify or stop the study based upon an evaluation of emerging safety data, in particular Adverse Events of Special Interest as outlined in [Section 10.1.3](#). Additional regular or ad-hoc safety reviews will be scheduled as recommended by the SMC.

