10.1.3 Adverse Events of Special Interest

An adverse event of special interest is one of scientific and medical concern specific to the Sponsor's product or program where ongoing monitoring and rapid communication by the Investigator to the Sponsor may be appropriate. These adverse events may be serious or non-serious. Applicable adverse events may require further investigation in order to characterize and understand them, and depending upon the nature of the event, rapid communication by the trial Sponsor to other parties may also be required. These adverse events of special interest must be reported using the same mechanism and timeframe (i.e. within one working day of the Investigator's or delegate's knowledge of the event) as described for serious adverse events in [Section 10.3](#). The adverse events of special interest include the following:

- Endophthalmitis
- 4+ ocular inflammation
- 2-3+ ocular inflammation that fails to decrease to 1+ or less within 30 days of the onset of the event
- Sustained (> 5 minutes) loss of light perception after APL-2 injection
- Sustained elevation of IOP (30 mmHg) at/past 90 minutes post-injection
- Any elevation of IOP requiring surgical intervention (i.e. paracentesis)
- New vitreous hemorrhage of > 2+ severity that does not resolve within 14 days of the onset of the event
- Progression to exudative AMD in the study eye or fellow eye requiring **surgical** intervention (see note below).

If an adverse event of special interest occurs in a study subject, the study subject will be followed for resolution of the adverse event. A decision will be made by the Sponsor concerning further exposure to the study treatment and further participation in the study.

Note: Intravitreal administration of anti-VEGF agents are **not** considered surgical interventions.

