### **4.3. SAFETY ENDPOINTS**

#### **4.3.1. Adverse Events**

The primary safety endpoints for the study are the number and severity of treatment emergent adverse events (TEAEs) and adverse events of special interest (AESI). AESI will be identified on the eCRF at the time of reporting and include:

- Endophthalmitis
- 4+ ocular inflammation
- 2-3+ ocular inflammation that fails to decrease to 1+ or less within 30 days of the onset of the event
- Sustained (> 5 minutes) loss of light perception after APL-2 (or Sham) injection
- Sustained elevation of IOP (30 mmHg) at/past 90 minutes post-injection
- Any elevation of IOP requiring surgical intervention (i.e. paracentesis)
- New vitreous hemorrhage of > 2+ severity that does not resolve within 14 days of the onset of the event
- Progression to exudative (wet) AMD in the study eye or fellow eye requiring surgical intervention (Note: Intravitreal administration of anti-VEGF agents are not considered surgical interventions.)

A clinical review of all ocular AEs will be performed prior to database lock to ensure all AESI have been identified.

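### New exudation on APL-2, the only safety imbalance the documents report, counts as an event of special interest only if it needs surgery

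*Protocol*

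**What the plan says.** **The signal.** Protocol 4.3 describes a Safety Monitoring Committee review of data as of 5 April 2017, at which "an imbalance in new exudation in subjects treated with APL-2 was observed". It adds: "Higher rates in new exudation were observed in eyes treated with APL-2, particularly monthly". The protocol carrying this text is "POT-CP121614 / Version 3.0 / 1 May 2017", so it was issued after the signal was known.

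**The AESI definition and list.** Protocol 10.1.3 opens: "An adverse event of special interest is one of scientific and medical concern specific to the" sponsor's product or programme, where rapid communication may be appropriate. The list then includes "Progression to exudative AMD in the study eye or fellow eye requiring" surgical intervention, with a note that anti-VEGF injections do not qualify. Protocol 10.5 repeats the restriction. SAP 4.3.1 carries the same entry: "requiring surgical intervention (Note: Intravitreal administration of anti-VEGF agents are not considered surgical interventions". Protocol 4.1.1 says that anti-VEGF agents "are the current standard-of-care for the treatment of exudative AMD".

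**What AESI status brings.** AESIs reach the sponsor within one working day (Protocol 10.1.3). The committee is to weigh emerging safety data, "in particular Adverse Events of Special Interest" (Protocol 8.2). The SAP names AESIs beside TEAEs as primary safety endpoints (4.3.1) and gives them their own summaries and listing (11.1). For the Month 12 report, SAP 12 includes SAEs and AESIs up to the last subject's Month 12 visit date; other data stop at each subject's own Month 12 visit.

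**What happens otherwise.** Under Protocol 10.5, progression that needs an intervention such as anti-VEGF is entered in the CRF as an adverse event. Progression that needs none is not an adverse event.

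**The concern.** The AESI category exists to give product-specific concerns quick reporting and a visible place in the results. The one concern that the protocol itself reports is admitted only in a form that its own account of standard care makes unlikely. Three things are at stake:

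- how quickly the sponsor hears of each new case;
- whether the special-interest tables show the exudation that occurs;
- whether cases arising after a subject's own Month 12 visit reach the CSR or only the 18-month addendum.

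A further gap lies underneath. SAP 4.2.2 identifies macular neovascularization (MNV) by reviewing ocular adverse events before database lock, so a case never recorded as an adverse event cannot be found that way.

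**Working it through.** The plan states no figure on this point, so the check is mainly a tracing of routes.

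**Step 1. Follow a new study-eye exudation through the documents.**

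| Type of case | Recorded as AE | Stated time limit | TEAE tables | AESI tables | In the CSR if it arises after the subject's own Month 12 visit |
|---|---|---|---|---|---|
| Serious (Protocol 10.1.2) | yes | 24 hours (10.3) | yes | only if surgical | yes, as SAE |
| Non-serious, surgery required | yes | one working day (10.1.3) | yes | yes | yes, as AESI |
| Non-serious, anti-VEGF | yes (10.5) | none | yes | no | not assured |
| No intervention | no (10.5) | none | no | no | no |

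The third row is where standard care would place most non-serious treated cases. For that row SAP 2 says only that later follow-up data on key safety outcomes may be presented. The fourth row is also invisible to the MNV analysis in SAP 8.2.2.

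**Step 2. Scale, on assumed rates.** Inputs: n = 80 subjects in each APL-2 arm (SAP 3.3), exudation rate p (assumed) and share of cases needing surgery s (assumed).

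- Expected cases = n × p
- Expected AESIs = n × p × s
- Chance of no AESI = (1 − p × s)^n

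| p | Cases | AESIs, s = 5% | Chance of none | AESIs, s = 10% | Chance of none |
|---|---|---|---|---|---|
| 5% | 80 × 0.05 = 4 | 0.2 | 0.9975^80 = 82% | 0.4 | 0.995^80 = 67% |
| 10% | 80 × 0.10 = 8 | 0.4 | 0.995^80 = 67% | 0.8 | 0.99^80 = 45% |
| 20% | 80 × 0.20 = 16 | 0.8 | 0.99^80 = 45% | 1.6 | 0.98^80 = 20% |

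If no case needs surgery, the AESI count from exudation is 0 at every rate.

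**Step 3. How far the MNV comparison compensates.** This is exact power of Fisher's test, 80 against 80, at the plan's two-sided 0.1 level, with every case recorded as an adverse event. All rates are assumed.

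| Sham rate | Power at 10% on APL-2 | Power at 20% on APL-2 |
|---|---|---|
| 1% | 75% | over 99% |
| 3% | 45% | 96% |
| 5% | 23% | 87% |

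The comparison is a real safeguard when the excess is large. It is weaker for a moderate excess, and weaker still if untreated cases go unrecorded.

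**The case against.** The other side has a good deal to say.

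- **The restriction is deliberate.** It is stated in three places and was kept after the signal was known. The definition is permissive: rapid communication *may* be appropriate. A reader might infer that the definition and the list contradict each other. They do not, strictly. The list leaves out an event that fits its own definition, and neither document says why.
- **The primary safety endpoint still counts these events.** A reader might infer that exudation drops out of it. The protocol's endpoint is TEAEs (5.4), the SAP's is TEAEs and AESIs, and treated exudation is a TEAE under both. Only the AESI summaries lose it.
- **MNV has its own analysis.** SAP 8.2.2 gives incidence, exposure-adjusted incidence, a test against sham, and a repeat by fellow-eye CNV at baseline, which is the risk factor that Protocol 4.3 raises.
- **Oversight did not depend on AESI status.** The committee reviews cumulative unmasked safety data, and its routine review found this imbalance. Serious cases, including important medical events, go within 24 hours.
- **Some relevant text is not in hand.** Protocol 4.3 refers to an Investigator Brochure addendum for details.

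All of this stands, and it narrows the point. It does not supply a deadline for non-serious anti-VEGF-treated cases, put them in the AESI tables or extend the data cut to them. Nor does it make untreated cases recordable. A later sentence of Protocol 10.5 leaves room for progression attributable to the test article, but it sits uneasily with the flat statement that progression without intervention is not an adverse event.

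**Conclusion.** The point holds in a limited form. Non-serious study-eye exudation treated with anti-VEGF is handled as an ordinary adverse event, although exudation is the only safety imbalance the documents report. It misses the one-working-day route, the AESI summaries and listing, and the SAP 12 data-cut exception. It remains visible in the TEAE tables and in the MNV comparison. Untreated exudation can be missed by both.

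A reader might also infer that the committee found no other imbalance, or that the harm is hidden from the report as a whole. The documents support neither.

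The size cannot be fixed from the documents, which give no exudation rate and no share needing surgery. On assumed exudation rates of 5% to 20% in an arm of 80, with 5% of cases needing surgery, 4 to 16 cases would give 0.2 to 0.8 expected AESIs. These counts are illustrative only.

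**What to change.** For reporting and tabulation only:

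1. In Protocol 10.1.3 and SAP 4.3.1, list new study-eye exudation as an AESI however it is managed.
2. Reconcile Protocol 10.5 with this, covering both the surgical restriction and the statement that progression without intervention is not an adverse event, so that every such case is recorded. Without this step, the pre-lock review of ocular adverse events cannot recover untreated cases.
3. In SAP 11.1, show new study-eye exudation as its own line in the treatment-emergent AESI tables.
4. Apply the SAP 12 data-cut exception to it.

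SAP V3.0 was written after the 12-month results were reviewed, so any tabulation added now should be labelled as added. By then the Month 12 visits were over, so faster reporting helps only during the remaining follow-up; the tabulation can still serve the 18-month addendum.

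The cost is one rapid report per event, a small eCRF change (AESIs are flagged there at reporting), and a higher AESI percentage in the APL-2 arms. Protocol 10.1.3 also ties AESI status to a sponsor decision on further exposure. Whether that sentence applies to these events is for the sponsor and the committee to reconcile.
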